## Demographic Characteristics of Study Sample Required for Clinical Trials

	Baseline A	Intervention	Baseline B	Totals
Enrolled	63	50	14	127
Completed	62	47	13	122
Lost to Follow-up	1	3	1	5
Under 18 Years of Age	0	0	0	0
Between 18 and 65	37	26	10	73
Over 65	26	24	4	54
Female	28	21	6	55
Male	35	29	8	72
American Indian, Alaskan	5	6	2	13
Asian	0	0	0	0
Hawaiian or Islander	1	0	0	1
Black or African American	0	0	0	0
White	56	43	11	110
More than one race	0	0	0	0
Unknown or Not Reported	1	1	1	3
Subtotal	63	50	14	127
Hispanic or Latino	0	0	0	0
Not Hispanic or Latino	61	47	11	119
Unknown or Not Reported	2	3	3	8
Subtotal	63	50	14	127

In addition, Table 3 presents the number of patients excluded by criterion and Table 4 shows the number of patient enrolled in the study from each county by experimental condition.

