### ***Design***

We used a quasi-experimental time series design with switching replications (Cook & Campbell, 1984). This design involved starting enrolled patients from each of the four counties in a baseline condition. Then, once a stable rate of enrollment had been reached, the introduction of the experimental procedures was staggered across patients from each county over time. That is, all patients from one county were enrolled into the intervention while those from the other counties remained in baseline. Later, patients from a second and third county were added to the intervention condition while those from the remaining county remained in baseline; and so on. Finally, a return to baseline condition was initiated for patients from all

four counties. This design protects against most threats to the internal validity of findings and many threats to their external validity. It is particularly helpful in protecting against threats posed by seasonal variables. A final "return to baseline" phase was also included in the study to add to protections from threats posed by interactions.

**Baseline and experimental conditions.** Patients in baseline conditions received the standard discharge services. Patients enrolled in the experimental condition received the standard discharge services and the Enhanced Discharge Planning and Rural Transition Supports.

**Measures.** All patients completed the PAM10 (Hibbard & Mahoney, 2005) and provided selected demographic information at the time of enrollment. Other demographic information was collected from each enrolled patient's medical record. In addition, we collected the LACE+ rating from the medical record and the rating of needs from our Rural Transition Needs Assessment. The LACE+ is a compilation of medical and treatment factors (e.g., chronic conditions, previous hospitalizations) derived from a patient's medical record that are used to assess risk for re-hospitalization (van Walraven, Wong, & Forster, 2012).

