#### 1) Hospital re-admissions

##### a) Number of hospital admission

i) H0i: There is no difference in the cumulative number of hospital admissions for day i (null hypothesis); H1i: The cumulative number of hospital admissions for the standard discharge group is greater than that for the enhanced discharge group; for days  $i = 3, 7, 14, 21, 30, 60, 90$ .

ii) We will assess the groups for differences using Poisson regression model.

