  - b) We will use a repeated measures ANOVA model (over the 7 time periods) to model the SF-12 Physical Health score as a function of treatment group.
- 5) Mental Health as measured by the Short Form (SF12) Mental Health Score
- a) Hoi: There is no difference in mean SF-12 Mental Health scores between the standard and enhanced discharge groups (null hypothesis); H1i: The mean SF-12 Mental Health scores differ between the standard and enhanced discharge groups.
  - b) We will use a repeated measures ANOVA model (over the 7 time periods) to model the SF-12 Mental Health score as a function of treatment group.
- 6) Care Transition Measure (CTM3) of discharge coordination services
- a) Hoi: There is no difference in mean CTM3 scores between the standard and enhanced discharge groups (null hypothesis); H1i: The mean CTM3 scores differ between the standard and enhanced discharge groups.
  - b) We will use a repeated measures ANOVA model (one time period at 3 days post discharge) to model to assess these hypotheses.
- 7) Rural Transition Measure (RTM14) of the delivery of transition services and supports
- a) H0: There is no difference in the mean RTM14 score between the standard and enhanced discharge groups (null hypothesis); H1: Patients in the enhanced discharge group will have a higher mean RTM14 rating than patients in the standard discharge group.
  - b) We will use a repeated measures ANOVA model (over the 6 time periods) to model the RTM14 score as a function of treatment group.

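### Condition followed county and calendar period, not randomisation, but no model includes a patient-level prognostic covariate, although LACE+, PAM10 and age were collected

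*Combined protocol and SAP*

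**What the plan says.** **Allocation.** The Design section states: "We used a quasi-experimental time series design with switching replications". At the first step of the stagger, "all patients from one county were enrolled into the intervention while those from the other counties remained in baseline". Further counties followed, and finally all four returned to baseline.

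**What was collected.** Under Measures, "All patients completed the PAM10" at enrolment, with selected demographic information. The next statement is that "we collected the LACE+ rating from the medical record and the rating of needs from our Rural Transition Needs Assessment". LACE+ is described as a compilation of medical and treatment factors "that are used to assess risk for re-hospitalization". Table 2 gives age in bands by condition.

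**What is modelled.** For the number of admissions (SAP item 1a): "We will assess the groups for differences using Poisson regression model". The logistic analyses are worded in the same way. For the SF-12 (item 4), the repeated-measures ANOVA is "to model the SF-12 Physical Health score as a function of treatment group", and item 5 repeats this for mental health. Nowhere does the SAP name a covariate, weighting, matching, stratification or a check of baseline balance.

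**The concern.** The primary question is whether the intervention changes the frequency of hospitalisations and emergency department visits. Condition was decided by where a patient lived and when the patient was admitted, so it was settled before consent. Of the 181 patients who met the criteria (127 enrolled plus 54 who declined), 54 (29.8%) declined, and the documents do not split them by condition. Nothing in this process balances individual prognosis.

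The study nevertheless holds a rating built to predict one of the primary outcomes, and the SAP does not use it. If one condition drew patients with more chronic illness or more previous admissions, a group-only model would report that difference as benefit or harm. This is distinct from the absence of county and calendar terms: two patients from one county in the same month can have very different LACE+ ratings.

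**Working it through.** The documents state no alpha, power, expected event rate or effect size, so there is no design figure to reproduce. Three checks were made.

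**1. Covariates named in each model (SAP items 1 to 7)**
- Items 1a, 2a, 3a: Poisson regression, groups compared; none named.
- Items 1b, 2b, 3b: logistic regression, groups compared; none named.
- Items 4, 5, 7: repeated-measures ANOVA with treatment group as the only named predictor.
- Item 6: ANOVA at one time point; none named.

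**2. What the tables show about case mix.** Table 2 gives "Enrolled 63 50 14 127" for Baseline A, intervention, Baseline B and total. I take the standard group to be both baselines: 63 + 14 = 77, against 50 enhanced.
- Over 65: standard (26 + 4)/77 = 39.0%; enhanced 24/50 = 48.0%; difference 9.0 points. With cells 47, 30, 26, 24: chi-square = 127 × (47×24 − 30×26)² / (77×50×73×54) = 1.01 on 1 df, p = 0.31.
- County (Table 4; Sanders, Beaverhead, Powell, Lake): standard 14, 8, 13, 42; enhanced 21, 8, 6, 15. Chi-square = Σ(O−E)²/E = 11.55 on 3 df, p = 0.009. Sanders is 18.2% against 42.0%, Lake 54.5% against 30.0%.
- LACE+ and PAM10: not reported by condition.

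The conditions clearly differ in geography. That shows allocation produced different mixes of patients, but it says nothing about which mix carried more risk.

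If patients over 65 had an admission risk 20 to 30 points higher (assumption), the age gap would shift the group difference by 0.09 × 0.20 = 1.8 to 0.09 × 0.30 = 2.7 points, against the enhanced group. For scale, at an assumed event rate of 20% to 30%, the standard error of a 77 v 50 comparison is √[p(1−p)(1/77 + 1/50)] = 7.3 to 8.3 points. The shift is therefore roughly 0.2 to 0.4 of one standard error.

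**3. Illustration of what an imbalance in risk would do.** Logistic regression was simulated with 77 v 50 patients, no true effect and 4,000 runs per setting. All of the following are assumptions: one-sided alpha 0.05, standard-group readmission 20% to 30%, and a normally distributed risk score with an odds ratio of 1.5 to 2.5 per SD.

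| Enhanced cohort's mean risk | Unadjusted odds ratio | False positives, unadjusted | False positives, adjusted |
|---|---|---|---|
| Equal | 1.00 | 4.4% to 4.9% | 4.4% to 5.3% |
| 0.25 to 0.5 SD lower | 0.91 to 0.66 | 6.6% to 21.6% | 4.1% to 5.2% |
| 0.25 SD higher | 1.10 to 1.22 | 1.4% to 2.4% | 4.3% to 4.9% |

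In the last row a real benefit would be partly hidden. The simulation lets the score carry the whole imbalance, so it shows the most that adjustment can achieve.

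**The case against.** **The design already protects validity.** The stagger gives some concurrent baseline patients, and the return to baseline adds a second comparison, so it would be unfair to call the conditions simply one cohort after another. That stands as a description of the design. But no model contains county or period, so the analysis does not use the protection, and such terms would not capture differences between patients within a county and period.

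**Silence is not exclusion.** True: the SAP does not forbid covariates. Leaving them open, however, allows the choice to be made after results are seen.

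**LACE+ may not be a clean covariate.** A reader might infer that LACE+ exists for every patient. The text says so expressly for PAM10 only. LACE+ comes in a separate sentence, paired with the needs rating, which the Procedures describe for intervention patients only (and which therefore cannot serve for adjustment). Complete LACE+ is a reasonable reading, not a stated fact. When it was scored is also not stated; it includes treatment factors, and the intervention began in hospital. This objection stands and shapes the fix.

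**No imbalance in risk has been shown.** Correct. The age gap is small, compatible with chance, and points away from false benefit if older means riskier.

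**Conclusion.** The point holds as a gap in specification that should be closed: allocation was not random, and no model carries a patient-level prognostic covariate although suitable ones were collected. Any systematic case-mix difference goes into the group comparison uncorrected. Its size and direction are unknown from the documents; the figures in the simulation depend on assumed imbalances.

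Two stronger readings are not supported. First, a reader might infer that case mix has produced an apparent benefit. Nothing reported shows this, and the false-positive rates of about 7% to 22% require a lower-risk enhanced cohort, the opposite of what the age split would suggest if age raises risk. Second, a reader might take the 95% limit for chance imbalance in a trait held by half the patients, 1.96 × 0.5 × √(1/77 + 1/50) = 17.8 points, multiply it by a 20 to 30 point risk gap, and call the resulting 3.6 to 5.3 points bias. Chance imbalance of that kind is already reflected in the standard error of the comparison; only systematic imbalance is bias.

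**What to change.** - **Items 1 and 2:** make the Poisson and logistic models with LACE+ (continuous) and age the main analysis, with the unadjusted estimate beside them. PAM10 is left out here to keep the list short where events may be few, and because the documents link LACE+, not PAM10, to re-hospitalisation.
- **Sparse events:** fix a rule in advance, for example LACE+ only when total events at that day fall below a stated number such as 30 (ten for each of the three slopes: group, LACE+ and age).
- **LACE+ values:** state a rule for missing ratings, and use only a value that the intervention cannot have affected.
- **Items 4 and 5:** add LACE+, PAM10 and age.
- **Items 3, 6 and 7:** say whether covariates apply.
- **Reporting:** tabulate LACE+ and PAM10 by condition.
- **Status:** the document already reports enrolment and completion counts. If outcomes have been examined, label the adjusted analysis post hoc.

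The change uses data the study reports having collected and costs one to three degrees of freedom per model. It does not replace county or calendar-period terms. Nor does it supply a baseline SF-12, which the first questionnaire at day 3 after discharge cannot provide.

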### ***Statistical Analysis Plan***

The primary hypotheses address the question of whether the intervention makes a difference in the frequency of hospitalizations and emergency department visits. There are at least two ways to view the measurement of these outcomes. The first is to examine the total number of hospital or emergency department visits in each condition. The second is to examine the proportion of patients who have at least one hospital or emergency department visits in each condition.

In addition, there are several intermediary outcomes we anticipate. These relate to the physical and mental health of patients, the rating of the quality of discharge planning services, and the rating of the delivery of rural transition services. We will test the following hypotheses using specified procedures:

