##### b) Proportion of patients with at least one hospital admission

i) H0i: There is no difference in the proportion of patients who report a hospital readmission for day i (null hypothesis); H1i: The proportion of patients who report a hospital readmission for the standard discharge group is greater than that for the enhanced discharge group; for days  $i = 3, 7, 14, 21, 30, 60, 90$ .

- ii) We will assess the groups for differences using logistic regression.
- 2) Emergency department visits
- a) Number of emergency department visits
    - i) H0i: There is no difference in the cumulative number of ED visits for day i (null hypothesis); H1i: The cumulative number of ED visits for the standard discharge group is greater than that for the enhanced discharge group; for days  $i = 3, 7, 14, 21, 30, 60, 90$ .
    - ii) We will assess the groups for differences using Poisson regression model.
  - b) Proportion of emergency department visits
    - i) H1i: The proportion of patients who report at least one ED visits for the standard discharge group is greater than that for the enhanced discharge group; for days  $i = 3, 7, 14, 21, 30, 60, 90$ .
    - ii) We will assess the groups for differences using logistic regression model.
- 3) Primary care provider (PCP) visits
- a) Number of PCP visits
    - i) H0i: There is no difference in the cumulative number of PCP visits for day i (null hypothesis); H1i: The cumulative number of PCP visits for the standard discharge group is greater than that for the enhanced discharge group; for days  $i = 3, 7, 14, 21, 30, 60, 90$ .
    - ii) We will assess the groups for differences using Poisson regression model.
  - b) Proportion of PCP visits
    - i) H0i: There is no difference in the proportion of patients who report at least one PCP visits for day i (null hypothesis); H1i: The proportion of patients who report at least one PCP visits for the standard discharge group is greater than that for the enhanced discharge group; for days  $i = 3, 7, 14, 21, 30, 60, 90$ .
    - ii) We will assess the groups for differences using logistic regression model.
- 4) Physical health as measured by the Short Form (SF12) functional health score

- a) Hoi: There is no difference in mean SF-12 Physical Health scores between the standard and enhanced discharge groups (null hypothesis); H1i: The mean SF-12 Physical Health scores differ between the standard and enhanced discharge groups.

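### The two primary outcomes are spread over 28 comparisons, with no alpha, sidedness, decisive day or metric, success rule or multiplicity control

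*Combined protocol and SAP*

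**What the plan says.** The opening of the Statistical Analysis Plan makes hospital admissions and ED visits jointly primary: "The primary hypotheses address the question of whether the intervention makes a difference in the frequency of hospitalizations and emergency department visits". On how to measure them it says "There are at least two ways to view the measurement of these outcomes", then lists the total number of events and the proportion of patients with at least one. It does not rank the two.

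Items 1a and 2a (counts, Poisson regression) and 1b and 2b (proportions, logistic regression) then set hypotheses indexed by day, for days 3, 7, 14, 21, 30, 60 and 90. The alternatives are directional. Item 1a, for example, reads "The cumulative number of hospital admissions for the standard discharge group is greater than that for the enhanced discharge group". By contrast, items 4 and 6 are non-directional: "The mean SF-12 Physical Health scores differ between the standard and enhanced discharge groups" and "The mean CTM3 scores differ between the standard and enhanced discharge groups".

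Two related matters are also open:
- **Data source.** Under Measures, patients report ED visits and admissions at any hospital. Under Data collection, the same kinds of event are taken from Epic, but only for the participating hospitals. Items 1b and 2b refer to patient report (item 1b: "There is no difference in the proportion of patients who report a hospital readmission for day i"). Items 1a and 2a name no source.
- **Primary care visits.** Item 3 tests them in the same 2 x 7 layout ("The cumulative number of PCP visits for the standard discharge group is greater than that for the enhanced discharge group"). They are not among the primary outcomes. They are also absent from the intermediary outcomes, of which the plan says "These relate to the physical and mental health of patients, the rating of the quality of discharge planning services", adding the delivery of transition services.

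**The concern.** A primary hypothesis needs a rule that says when it has been met. Here each outcome can be judged on either metric, on any of seven days and, for the counts, from either source. Nothing says which result decides, or at what level. The plan therefore cannot return a clear negative answer to its own primary question, and a reader cannot tell a planned success from the best of 28 results. If each comparison is tested at a conventional level, a false benefit somewhere among them is several times more likely than that level suggests.

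**Working it through.** The plan has no sample-size, power or error-rate figure to reproduce, so the check is a count followed by a conditional calculation.

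**1. Count.** 2 outcomes x 2 metrics x 7 days = 28 primary comparisons. Primary care visits add 2 x 7 = 14 that are unclassified.

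**2. Independence reference.** 1 - 0.95^28 = 76.2%, and 1 - 0.975^28 = 50.8%. These overstate the risk, because the days are cumulative and the two metrics share the same events.

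**3. Simulation that allows for this correlation.**
- *From the documents (Table 2):* Baseline A and B pooled against intervention, 63 + 14 = 77 v 50 enrolled, or 62 + 13 = 75 v 47 completed.
- *Assumed:* no true effect; a constant event rate over 90 days; mean admissions/ED visits per patient of 0.2/0.3, 0.3/0.4 or 0.5/0.7; no patient heterogeneity; no county or period effects; cumulative proportions. A Wald test with a zero-event condition counts as no rejection.

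Chance of at least one false benefit among the 28, with admissions and ED visits independent (10,000 trials per scenario, three rate pairs in that order):

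| Patients | Per-test level | Wald | Score |
|---|---|---|---|
| 77 v 50 | one-sided 5% | 18.0 / 21.8 / 28.0% | 25.8 / 29.2 / 33.9% |
| 77 v 50 | one-sided 2.5% | 7.8 / 10.5 / 14.0% | 14.3 / 16.2 / 19.2% |
| 75 v 47 | one-sided 5% | 17.4 / 21.4 / 26.8% | 25.6 / 28.5 / 32.5% |
| 75 v 47 | one-sided 2.5% | 6.7 / 8.9 / 12.9% | 13.6 / 14.9 / 18.0% |

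**4. Overlap between the outcomes.** An ED visit that ends in admission would count in both, and the documents give no overlap rate. At one-sided 5%:
- If 80% of admissions also count as ED visits: about 15-24% (Wald) and 22-28% (score).
- If all do: about 14-21% (Wald) and 19-25% (score).

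At one-sided 2.5% with full overlap the low end is about 6%. Simulation error is about one percentage point.

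**5. Combined range.** 14-34% at one-sided 5% (14/5 = 2.8 to 34/5 = 6.8 times nominal) and 6-19% at one-sided 2.5% (6/2.5 = 2.4 to 19/2.5 = 7.6 times).

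**6. Sensitivity (outcomes independent).** Dropping days 3 and 7 lowers the one-sided 5% figures by only 0-0.3 points (Wald) or 0.5-3.1 points (score). Items 1b and 2b do not say that the proportions are cumulative. Read per reporting interval, the ranges become 17-47% and 5-27%, but that calculation does not separate out the effect of sparse data.

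**The case against.** Four arguments can be made for the plan.

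*The comparisons are highly correlated.* This is true, and it rules out the 76% figure, which a reader might infer from 28 tests at 5%. It assumes independence that cumulative data cannot have. Inflation remains after the correlation is allowed for. Overlap between admissions and ED visits lowers it further, which is why the range starts at 14% and 6%.

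*The seven days only describe a trajectory.* The text does not support this. Each day has its own hypotheses, the plan says that they will be tested, and no day is called descriptive.

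*The directional alternatives settle sidedness.* A reader might infer one-sided tests. The documents state neither the sidedness nor the level of any test, and the opening sentence asks only whether there is a difference.

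*The study is already enrolled, so a new rule comes too late.* This stands in part. The Patient Population section and Table 2 report enrolment and completion as finished. A reader might infer that the outcomes had been seen and a favourable result picked. The documents contain no outcome data and no evidence of selection, so that inference is not supported. It does limit the remedy: a rule chosen after outcomes are seen does not protect the error rate.

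**Conclusion.** The omission is certain on the text: 28 primary comparisons and no rule for deciding among them. It must be fixed, because the plan as written cannot say whether the intervention succeeded.

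The size is conditional: about 14-34% at one-sided 5% per test and 6-19% at one-sided 2.5%. The upper ends assume that admissions and ED visits are independent and use score tests; Wald tests reach about 28% and 14%. The lower ends assume that every admission also counts as an ED visit and use Wald tests. The plan names neither test.

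These figures isolate multiplicity in an idealised comparison of individuals. They should not be read as this study's actual error rate. The Design section introduces the intervention by county over time, and county or period effects, or differences between patients in event rate, could push the figures higher.

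Two side matters do not change the count. Item 2b lacks a null hypothesis, which is a drafting slip. Primary care visits are not named as primary and so are not among the 28.

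**What to change.** - State the total alpha and the sidedness of the tests.
- For each primary outcome name one metric, one day and one data source (patient report or Epic). Two workable examples are the proportion with at least one event from discharge through day 90, by logistic regression, or the day-90 count with a robust or over-dispersed variance.
- Test the two outcomes with Holm at the stated total alpha, and claim success for an outcome only if its Holm test rejects.
- Label the other 28 - 2 = 26 comparisons and the 14 primary care comparisons secondary, with confidence intervals and no significance claim.
- Say when the choice was made and whether outcomes had been seen. If they had, report all 28 results and describe them as exploratory.

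A null simulation of the Holm rule (outcomes unseen, total one-sided 5%, gamma frailty variance 0 to 2) gave 3.4-5.2% for two day-90 proportions and 3.7-6.0% for two counts with robust variance. Plain Poisson counts gave 5.6-14.8% under frailty variance 1 to 2, so the plain count is not offered.

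The cost is SAP text, some power, and the loss of primary claims at other days. The first Holm step halves alpha. Take an assumed 0.30 v 0.15 with 77 v 50 patients:
- Pooled proportion = (77 x 0.30 + 50 x 0.15)/127 = 0.241.
- Null SE = sqrt(0.241 x 0.759 x (1/77 + 1/50)) = 0.0777.
- Alternative SE = sqrt(0.30 x 0.70/77 + 0.15 x 0.85/50) = 0.0726.
- Power = Phi((0.15 - z x 0.0777)/0.0726), which is 62% at one-sided 0.05, 49% at 0.025 and 37% at 0.0125.

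With 75 v 47 completers the figures are 60%, 47% and 35%. A proportion also ignores repeat events, which matters for a question about frequency.
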